The HepQuant SHUNT Liver Diagnostic Kit for Likelihood of Large Esophageal Varices: The SHUNT-V Study

SHORT TITLE: The SHUNT-V Study for Varices

Protocol Number: HQ-US-SHUNT-1801 National Clinical Trial (NCT) Identified Number: NCT03583996 Principal Investigator: TBD IDE Sponsor: HepQuant LLC Funded by: HepQuant LLC Version Number: 2.4 6 October 2020

Summary of Changes from Previous Version 2.3 to new Version 2.4:

Affected Section(s)	Summary of Revisions Made	Rationale
All	Updated Headers and Footers with current revision and date	Protocol Version 2.4 introduction
1.1, 9	Definition of False Negative Rate (FNR) in the protocol clarified	FNR was defined contextually but not explicitly, added explicit definition for sake of clarity, as well as a discussion of differences in terminology for FNR between the literature and FDA guidance.
1.1, 3, 4.1.3, 4.3.2, 9.4.3, 9.6.2	Addition of "miss rate" to the list of results that will be analyzed and reported for the study	To address discrepancies in calculation of FNR between published literature and FDA guidance.

1.1, 3, 9, 9.1.1, 9.5	Performance criteria for sensitivity added to primary endpoint	Ensuring that the FNR is not unacceptably high when NLR < 0.52
1.3, 1.4, 4.1.3, 8.1	Updated to indicate that MELD and CP scores are calculated automatically from lab results	Clarification that study site personnel are not required to manually calculate MELD or CP scores.
1.3	Clarification that Visit 3 physical exam is symptom-directed	Consistency with rest of protocol
1.4, 8.1	Added instruction to upload EGD reports and images into EDC system	Consistency with design of EDC system
4.1.1, 5	Changed total number of subjects from "A total of 420" to "Up to 420"	Updates related to introduction of interim analysis
4.1.3	Description of interim analysis added	Introduction of interim analysis
5	Number of sites updated	Reference missed in earlier updates to protocol when site number was increased from 20 to 40
5.5	Study duration updated	Updated to reflect actual length of study recruitment
6.6	Removed reference implying HepQuant would be blinded to DSI results	HepQuant cannot be blinded to DSI results as HepQuant's laboratory is the only facility capable of analyzing subject samples
8.1	References to Karnofsky performance status removed	Correction. Requirement was removed in an early edit to the protocol but these references were missed in that update.
8.1	Updated description of scheduling status of EGD to include subjects in the process of being scheduled for EGD.	Consistency with remainder of protocol
9.2.1	Description of simulation study added	Simulation study performed to demonstrate adequate power

9.2.1	Reference to check of prevalence after 300 subjects removed	Obviated by introduction of Interim Analysis.
9.2.1	Added reference to interim analysis at 250 subjects	Introduction of Interim Analysis necessitated change
9.2.2	Description of analysis of secondary endpoints updated to reflect potential for early termination	Introduction of Interim Analysis necessitated change
9.3	Description of analysis population updated to include references to 250 subjects minimum	Introduction of Interim Analysis necessitated change
9.4.2	Completely rewritten to describe the analysis of the primary endpoint with the addition of the interim analysis and the performance criteria for sensitivity	Introduction of Interim Analysis necessitated change
9.4.3	Significant rewriting and moving content to better support description of interim analysis	Introduction of Interim Analysis necessitated change
9.5.1	New section to describe interim analysis, including initial and final goals and decision criteria (including a binding futility assessment), as well as the processes, controls, and rationale for the introduction of the interim analysis.	Introduction of Interim Analysis necessitated change
9.6.1.2	Minimum size for subgroup analysis changed from 100 to 50 subjects	To account for potential for smaller subsets due to introduction of interim analysis
9.6.2	STAT performance goal updated	Accounting for change in statistical methodology due to introduction of interim analysis
10.1.2.2	Conditions under which study will be stopped updated to include a finding of futility at the interim analysis	Acknowledgement that the assessment for futility described in Section 9.5.1 is binding.

10.2.1	Composition updated	of	committee	membership	Adjusting for changes in staffing
--------	------------------------	----	-----------	------------	-----------------------------------

Table of Contents

1	PROTOCOL SUMMARY	4
1.1	Synopsis	4
1.2	Study Flow Diagram	8
1.3	Visit Schedule and Procedures	9
1.4	Schedule of Activities (SoA)	
1.5	Flow Chart of Procedures	
2	INTRODUCTION	13
2.1	Study Rationale	
2.1.1	Statement of Problem and Filling an Unmet Need	13
2.1.2	Study Population and Disease	14
2.1.3	Pitfalls of Current Practice	14

The trial will be conducted in accordance with the applicable United States (US) laws under the Food, Drug, and Cosmetic Act and implementing regulations under Title 21 of the Code of Federal Regulations (CFR).

The Principal Investigator will sign an investigator's agreement, written per FDA guidelines (Appendix A), that no deviation from, or changes to the protocol will take place without prior agreement from the Investigational Device Exemption (IDE) Sponsor and documented approval from the Institutional Review Board (IRB), except where necessary to eliminate an immediate hazard(s) to the trial participants.

The protocol, informed consent form, recruitment materials, and all participant materials will be submitted to the IRB for review and approval. Approval of both the protocol and the consent form must be obtained before any participant is enrolled. Any amendment to the protocol will require review and approval by the IRB before the proposed changes are implemented in the study. All changes to the consent form will be IRB approved; a determination will be made by the IRB regarding whether a new consent needs to be obtained from participants who provided consent, using a previously approved consent form.

1 PROTOCOL SUMMARY

1.1 Synopsis

Title: The HepQuant SHUNT Liver Diagnostic Kit for Likelihood of Large Esophageal Varices: The SHUNT-V Study

Study Description:

The **intended population** for the HepQuant SHUNT Liver Diagnostic Kit (test) is the population with chronic liver disease (CLD) characterized by having either biopsy-proven or clinical cirrhosis (Child-Pugh (CP) A or B), suspected cirrhosis based on surrogate tests for cirrhosis, or, advanced fibrosis with low platelet count, who are selected for future esophagogastroduodenoscopy (EGD) to screen for varices. The **intended use** is to provide the clinician with the likelihood of finding large esophageal varices if the EGD were to be performed. This information may aid the clinician in the decision to proceed with or avoid the EGD.

The purpose of this study is to validate the Disease Severity Index (DSI) from the HepQuant SHUNT Test for likelihood of large esophageal varices. Our **HALT-C Training dataset** demonstrated that the DSI 18.3 had sensitivity 95%, specificity 54%, positive predictive value (PPV) 19%, negative predictive value (NPV) 99%, negative likelihood ratio (NLR; equals ((1-sensitivity)/specificity)) 0.0926, and false negative rate (FNR = 1-NPV¹) 1% for large esophageal varices. This diagnostic performance compares favorably with published results from other tests or combinations of tests, such as FibroScan plus platelet count.

To validate DSI \leq 18.3 as a cutoff for cases not likely to have large esophageal varices, we will enroll 420 subjects with chronic liver disease (CLD) of mixed etiologies from no more than 40 USA clinical centers (**CLD Validation dataset**). These will be subjects who have already been selected for variceal screening or surveillance, but have not yet undergone the procedure. The targeted expected prevalence of large esophageal varices within the enrolled

¹ NOTE: There is some disagreement in the literature regarding the calculation of the False Negative Rate (FNR) for a test. FNR has been defined by the U.S. Food and Drug Administration in a disease-centric manner as 1 - Sensitivity ((Σ False negative) / (Σ Condition positive)), while being defined in much of the clinical literature in a test-centric manner as 1- NPV ((Σ False negative) / (Σ Predicted condition negative)). To compare to published results from the literature, in this protocol, the test-centric definition for FNR (1-NPV) has been used, and the term "miss rate" has been used to express 1-Sensitivity.

population is 20%. Each subject will have been selected to undergo a future EGD for variceal screening or surveillance according to standard criteria used in current clinical practice.

Enrolled subjects will undergo standard clinical assessment, laboratory tests, and the HepQuant SHUNT Test. The previously scheduled EGD will be performed no more than 6 weeks following the HepQuant SHUNT Test.

The relationship of DSI to large varices will be analyzed by AUROC and the diagnostic performance of the DSI cutoff \leq 18.3 will be defined by sensitivity, specificity, PPV, NPV, NLR, PLR, FNR and miss rate². The validated DSI cutoff will aid the clinician in the decision to proceed with or avoid the EGD.

Objectives:

The **primary objective** of this study is to validate DSI ≤18.3 for identifying subjects with CLD selected for future EGD for variceal screening or surveillance who are not likely to have large esophageal varices if the EGD were to be performed ("Rule Out").

The Secondary objective is to define the relationship of DSI to probability for large varices over the full range of DSI.

Exploratory objective 1 is to examine the diagnostic performance of DSI for large varices over the full range of DSI. We will generate and evaluate the AUROC (c-statistic) for DSI in likelihood of large esophageal varices. The AUROC for DSI in likelihood of large varices will be compared to the c-statistic 0.76 reported by Abrades, et al, for LSM plus platelet count (8).

In addition, we will examine the diagnostic performance (sensitivity, specificity, PPV, NPV, NLR, PLR, FNR) of DSI to define the optimal DSI for "Rule Out" – highest sensitivity and NPV with lowest FNR. We will also compare the diagnostic performance of this "optimum" DSI to DSI 18.3. The purpose of this analysis is to provide upside and downside performance of DSI around the validated cutoff of DSI 18.3.

This analysis will yield a table of sensitivities, specificities, NPVs, PPVs, NLRs, PLRs, FNRs, and miss rates² over the given range of DSI.

Exploratory Objective 2 (DSI for Small or Any Size of Esophageal Varices) is evaluation of the diagnostic performance of DSI for small esophageal varices and for esophageal varices of any size. The analyses listed above for the primary and secondary objectives and exploratory objective 1 will be repeated using small varices in one set of analyses and any size of varices in another set of analyses.

Exploratory Objective 3 is evaluation of the diagnostic performance of a single 60 minute time point (STAT) from the clearance curve of the orally administered d4-cholate. We will evaluate STAT's diagnostic performance for large, small, and any size of esophageal varices.

Endpoints:

The **endpoint** for the **primary objective** is the negative likelihood ratio (NLR) for large esophageal varices. The performance goal for validation of DSI \leq 18.3 is based on two requirements: (a) the upper limit of the confidence interval (CI) for NLR must rule out NLR > 0.52 and (b) the observed sensitivity must be > 0.85. The confidence level

² In this protocol, FNR is defined as 1-NPV and miss rate is defined as 1-Sensitivity. See the footnote in Section 1.1 for a discussion of these two measures.

for the confidence interval for NLR will be adjusted in order to maintain a one-sided type I error rate of 0.025 as described in section 9.5.1.

The **endpoint for the secondary objective** is the plot of predicted probability of large varices versus DSI using logistic regression analysis and affiliated statistical tests of the significance of the association between the continuous DSI score and risk of large varices. These analytical results will be evaluated using a calibration table in which the prevalence of large varices is tabulated by DSI quartile.

The **endpoint for exploratory objective 1** is the AUROC (c-statistic) and parameters for diagnostic performance of DSI in likelihood of large esophageal varices. The **endpoints** for **exploratory objective 2** are the c-statistics for the AUROCs for DSI in the likelihood of small or any size of esophageal varices. The **endpoints** for **exploratory objective 3** are the c-statistics for the AUROCs for STAT in the likelihood of large, small, or any size of esophageal varices. The c-statistics for STAT will be compared to the c-statistics for DSI.

Study Population:

This is a US multicenter study. Participants will have been diagnosed with CLD and have been scheduled for EGD for the indication of variceal screening or surveillance. The study will include both men and women, ages \geq 18 years, and all races and ethnicities; and, will comprise a broad clinical spectrum of CLD to include noncirrhotic F3 stage of fibrosis with low platelet count, compensated cirrhosis (Child-Pugh class A), and moderately decompensated cirrhosis (Child-Pugh (CP) class B cirrhosis). Child-Pugh (CP) class C cases and cases with prior variceal hemorrhage, refractory ascites, or refractory encephalopathy are excluded. The latter cases are at high risk for large esophageal varices and EGD screening for varices is strongly recommended without the need for additional testing.

Phase: Device, Pivotal Study

Description of Sites/Facilities Enrolling Participants:

This study will be conducted at not more than 40 USA clinical centers. The participating centers will utilize either local or central Institutional Review Boards (IRBs), have extensive experience in the care and management of patients with liver disease, and have effectively managed clinical trials.

Description of Study Intervention:

The HepQuant SHUNT Liver Diagnostic Kit contains one 20 mL vial of 25% human serum albumin, one 30 mL vial containing 10 mL of 40 mg cholate labeled with 4 deuterium atoms (d4-cholate) in sodium bicarbonate solution for oral dosing, one 10 mL val containing 5.5 mL of 22 mg cholate labeled with carbon-13 (13C-cholate) in sodium bicarbonate solution for intravenous injection (5.0 mL, 20 mg is injected),), a 3-way stopcock, pipettes, transfer tubes, instructions for use, labels, and materials for mailing serum to HepQuant's reference laboratory. Cholates and albumin are natural endogenous compounds of the human body. The labels, d4 and 13C, are cold stable labels and are NOT RADIOACTIVE. Deuterium and carbon-13 are naturally abundant in the human body – deuterium represents approximately 0.0156% of all hydrogen atoms and carbon-13 represents 1.1% of all carbon atoms. There is no significant increase in the body's pools of deuterium or carbon-13 from administration of doses of d4- and 13C-cholates used in the HepQuant SHUNT test.

The HepQuant SHUNT test measures liver function (cholate uptake), and physiology (hepatic and portal inflows and portal-systemic shunting) from simultaneous clearance of both the orally and intravenously administered d4and 13C-cholates. Six timed blood samples (3 mL each) are obtained at 0, 5±1, 20±2, 45±5, 60±5, and 90±5 minutes. Concentrations of d4- and 13C-cholate are measured by LC/MS, clearances defined, and hepatic filtration rates, SHUNT, STAT, and DSI calculated. DSI has a range from 0 to 50 based upon results from over 1600 tests in over 700 persons.

Study's Duration:

18-24 months

[figure not shown]
Participant's Duration:

[figure not shown]
From 3 to 100 days

Sample Size and Power:

The study will enroll no more than 420 subjects, to provide 80% probability (power) that the upper limit of the 95% CI for the observed NLR_0 is <0.52 for the DSI cutoff of 18.3 in identifying subjects unlikely to have large esophageal varices.

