9.2 Sample Size Determination

9.2.1 PRIMARY EFFICACY ENDPOINT: SAMPLE SIZE AND POWER

Based on NLR

The trial sample size was evaluated and selected to assure adequate statistical power that the upper limit of the 95% CI for NLR will be smaller than 0.52. For design purposes we evaluate power and sample size using the variance from Table 9 equation E under the hypothesis that NLR = 0.20 with sensitivity = 0.90, specificity = 0.50, and 20% prevalence of large varices (i.e., 80 subjects with large varices = 0.2x400). A sample size of 400 participants (80 with large varices, 320 without) was selected to provide adequate power based on the following power characteristics:

		Power	for variou	ıs sample	sizes
NLR	FNR	380	400	420	440
0.20	0.048	0.78	0.80	0.82	0.84
0.19	0.045	0.82	0.84	0.86	0.87
0.18	0.043	0.86	0.88	0.89	0.91
0.17	0.041	0.89	0.91	0.92	0.93
0.16	0.038	0.92	0.93	0.94	0.95
0.15	0.036	0.95	0.96	0.96	0.97

Table 10: Initial Power Analysis for Selection of N-400

In this analysis 400 subjects provide over 80% probability/power of rejecting the rule-out hypothesis of NLR > 0.52 when the true NLR is smaller than 0.20. From Table 9 equation D, NLR = 0.2 corresponds to FNR = 0.048; thus, the trial has more than 80% power for FNR smaller than 5%. With 400 subjects, the upper limit of the 95% confidence will exclude NLR > 0.52 if the NLR in the trial is smaller than 0.27; that is, the threshold (critical value) for rejecting the NLR null hypothesis is NLR≤0.27 (corresponding to FNR smaller than 6.5%). This evaluation is based on the large-sample variance of equation E and is adequate for selecting the total sample size for the trial. A complete power evaluation of trial power with and without an interim analysis requires a simulation study as described in section 9.5.1.

Based on Predictive Value of a Negative Test (NPV)

NPV is the probability that a subject with DSI \leq 18.3 does not have varices, and the false negative rate is defined from NPV according to equation D in **Table 9**. The goal is to ensure that *NPV is suitably large and FNR* is suitably small. NLR can also be written in terms of NPV. From equation D, *NLR* <0.27 corresponds to FNR <6.5% and a NPV over 0.937. Similarly, the critical value rules out NLR > 0.52, which corresponds to NPV > 0.885 (FNR < 11.5%). The study sample size gives 80% power under the hypothesis that *NLR* = 0.2, which corresponds to FNR < 5%.

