0.40	0.146	0.088	0.041	0.131	0.077	0.032
0.30	0.502	0.380	0.157	0.417	0.348	0.124
0.20	0.524	0.916	0.583	0.520	0.855	0.545
0.15	NA	0.930	0.910	NA	0.880	0.890
			25% prevalence o	f large varices		
0.52	0.021	0.021	0.012	0.019	0.017	0.010
0.40	0.170	0.107	0.054	0.151	0.100	0.041
0.30	0.515	0.462	0.193	0.450	0.422	0.172
0.20	0.515	0.944	0.696	0.523	0.888	0.668
0.15	NA	0.945	0.956	NA	0.902	0.951
	NA denotes combi	nations that produc	ce specificity = 1.0 a	and results that ca	nnot occur in a trial	

Table 12: Power for the SHUNT-V trial with and without interim analyses. The type I error rate is the power when NLR = 0.52 and is always smaller than the target one-sided 0.025 alpha level.

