In the case of the second conclusion, i.e., futility, the trial will be stopped; the assessment of futility represents a binding assessment.

In the case of the third conclusion, the trial will continue to the full sample of 400 subjects with complete data. If the study is not stopped early, then the full-sample (N=400) analysis will reach an efficacy conclusion if the upper limit of the 96.07% confidence interval is smaller than 0.52 and the observed sensitivity is greater than or equal to 0.85.

If the efficacy or futility decision criteria are satisfied, then HepQuant will request the analysis data set and analysis report from the independent statistician. HepQuant will reproduce the analysis from the independent statistician and initiate the trial termination processes. If neither the efficacy nor futility criteria are satisfied, then HepQuant will remain blinded and will not receive the results of the interim analysis. The independent statistician will archive the analysis and the interim analysis data set for reference upon trial completion.

The power and type I error rate using the above interim decision criteria have been evaluated in a simulation study as described in section 9.4.2 and summarized in **Table 12**. The simulation study also calculates the probability that the trial will satisfy the interim decision criteria. **Table 13** summarizes the chance of satisfying the interim efficacy and futility decision criteria as a function of the true NLR when true sensitivity is 90%.

	Decision	s at N=250	Decisions	at N=400	Total power
NLR	Futility	Efficacy	Futilty	Efficacy	for Efficacy
		20% prevale	nce of large v	arices	
0.52	0.744	0.004	0.241	0.011	0.015
0.40	0.521	0.022	0.403	0.055	0.077
0.30	0.220	0.124	0.433	0.223	0.348
0.20	0.118	0.652	0.027	0.203	0.855
0.15	0.120	0.880	0.000	0.001	0.880
		25% prevale	25% prevalence of large varices		
0.52	0.747	0.005	0.236	0.012	0.017
0.40	0.484	0.032	0.416	0.069	0.100
0.30	0.184	0.166	0.394	0.256	0.422
0.20	0.100	0.760	0.013	0.128	0.888
0.15	0.098	0.902	0.000	0.000	0.902

Table 13: Probability of reaching the futility and efficacy decisions at the interim (N=250) and full sample(N=400) analyses. Probabilities from simulations for the indicated NLR when sensitivity = 0.90.

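### The 80% power in the Synopsis and Section 9.2.1 belongs to a single-look, NLR-only 95% rule that the trial does not use, and the claim of more than 80% power for FNR below 5% fails at other sensitivities

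*Combined protocol and SAP*

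**What the plan says.** The power paragraph of the Synopsis (Section 1.1) says enrollment is set "to provide 80% probability (power) that the upper limit of the 95% CI for the observed NLR_0 is <0.52". It names no assumed NLR, sensitivity or specificity, no sensitivity goal and no interim look. The endpoint paragraph of the same section does state both performance goals, and says the confidence level is adjusted to "maintain a one-sided type I error rate of 0.025 as described in section 9.5.1".

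Section 9.2.1 sizes the trial so that "the upper limit of the 95% CI for NLR will be smaller than 0.52", "under the hypothesis that NLR = 0.20 with sensitivity = 0.90, specificity = 0.50, and 20% prevalence of large varices". Table 10 follows, titled as an initial analysis. Its last row reads "0.15 0.036 0.95 0.96 0.96 0.97" (NLR, FNR, then power at N = 380, 400, 420 and 440). The text then says "In this analysis 400 subjects provide over 80% probability/power of rejecting the rule-out hypothesis of NLR > 0.52" when the true NLR is below 0.20, and converts this into more than 80% power whenever FNR is under 5%. The section says equation E is adequate for choosing N and that a complete evaluation needs a simulation. Its closing NPV paragraph again credits the study sample size with 80% power, without that qualifier.

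Section 9.4.2 reports the simulation in Table 12. At 20% prevalence and NLR 0.15 the row is "0.15 NA 0.930 0.910 NA 0.880 0.890" (sensitivity 0.85, 0.90 and 0.95 without the interim, then the same with it). Section 9.5.1 sets interim efficacy at a 97.64% score interval with observed sensitivity of at least 0.85. Final efficacy requires "upper limit of the 96.07% confidence interval is smaller than 0.52 and the observed sensitivity is greater than or equal to 0.85". Futility is binding, and its two conditions (51.41% upper limit above 0.52; observed sensitivity below 0.85) are joined by 'and'.

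**The concern.** No look in the plan applies an unadjusted 95% interval for NLR on its own. The power statement and the success rule therefore describe different events, and a Synopsis reader has no signal of this because the 'initial' label appears only in Section 9.2.1.

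The same scenario also carries different powers in different places. Table 10 lies below Table 12 at the design point and above it at NLR 0.15, so it cannot be called uniformly conservative.

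The sentence tying power above 80% to FNR below 5% is the most exposed. FNR depends on NLR and prevalence only, whereas power under this rule depends strongly on how sensitivity and specificity combine to give that NLR. A sponsor, ethics board or regulator relying on the sentence would expect at least 80% power in scenarios where the plan's own simulation gives little more than 50%.

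**Working it through.** **Inputs.** Null NLR 0.52; N = 400 with 80 cases and 320 non-cases; sensitivity 0.90 and specificity 0.50 at the design point (Section 9.2.1); equation E (Table 9); interval levels and sensitivity goal (Section 9.5.1); simulated powers (Tables 12 and 13).

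**Step 1: reproduce Table 10.** Power = Φ[ln(0.52/NLR)/√V − 1.96], where V = sens/((1−sens)·80) + (1−spec)/(spec·320).

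- NLR 0.20 (0.90, 0.50): V = 0.1125 + 0.0031 = 0.1156, √V = 0.340; 0.9555/0.340 − 1.96 = 0.85; power 0.802 (stated 0.80).
- NLR 0.15 (0.90, 0.667): V = 0.1125 + 0.0016 = 0.1141, √V = 0.338; 1.2432/0.338 − 1.96 = 1.72; power 0.957 (stated 0.96).
- Critical value: 0.52·exp(−1.96 × 0.340) = 0.267 (stated 0.27).
- If NLR 0.15 is reached instead with specificity held at 0.50 (sensitivity 0.925), power is 0.880.

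Table 10 is therefore correct for its own method: one look, 95% Wald interval, NLR goal only, sensitivity fixed at 0.90.

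**Step 2: power of the trial's rule.** Simulation with 400,000 trials per scenario, a binomial number of cases, and the score test of miss rate = 0.52 × specificity. Looks are at N=250 (z = 2.264) and N=400 (z = 2.061), with observed sensitivity of at least 0.85. Futility was run two ways: either condition stops (OR), and both are required (AND, as written). All rows are at 20% prevalence.

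| NLR | Sens | Spec | Table 10 | Table 12, no interim | Table 12, interim | Simulated, OR | Simulated, AND |
|---|---|---|---|---|---|---|---|
| 0.20 | 0.90 | 0.50 | 0.80 | 0.916 | 0.855 | 0.85 | 0.915 |
| 0.15 | 0.90 | 0.667 | 0.96 | 0.930 | 0.880 | 0.88 | 0.95 |
| 0.20 | 0.85 | 0.75 | – | 0.524 | 0.520 | 0.52 | 0.63 |
| 0.20 | 0.95 | 0.25 | – | 0.583 | 0.545 | 0.54 | 0.54 |

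The OR version matches Table 12. It also matches Table 13: the probability of interim futility at sensitivity 0.90 is 0.745 at NLR 0.52 (stated 0.744) and 0.123 at NLR 0.20 (stated 0.118). The AND version gives 0.123 and 0.011.

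**Step 3: the FNR sentence.** By equation D at 20% prevalence, FNR = 1 − 1/(1 + 0.20 × 0.25) = 0.048 for NLR 0.20, whatever the sensitivity. The last two table rows have that same FNR, and their power is 0.52 to 0.63. At sensitivity 0.85 the sensitivity goal binds, because the true value sits on the threshold. At sensitivity 0.95 the NLR goal binds: few false negatives make the NLR estimate imprecise, and the sensitivity goal removes almost nothing. Equation E alone shows this second effect: V = 0.2375 + 0.0094 = 0.2469, √V = 0.497; 0.9555/0.497 − 1.96 = −0.04; power 0.485. The sentence therefore does not hold in general even under the method that produced it.

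**The case against.** The strongest reply is that the difference is disclosed. Table 10 is titled as initial, Section 9.2.1 says equation E serves to choose N, and Sections 9.2.1 and 9.4.2 both send the reader to the simulation. The endpoint paragraph of the Synopsis gives both goals and the adjusted confidence level. At the design point 80% is below the power on either futility reading, so sizing on it was safe. If the training-set performance held (sensitivity 0.95, NLR 0.0926), simulated power is at least 0.996 on either reading.

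Most of this stands. Table 10 contains no arithmetic error, and nothing here shows the sample size to be too small. What remains is that the Synopsis power sentence and the two unqualified sentences in Section 9.2.1 are outside the disclosure, and the FNR sentence is contradicted by Table 12.

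A reader might also infer that the risk of failing with a good test (NLR 0.15, sensitivity 0.90) is 12% rather than the 4% implied by Table 10. The documents do not support that as the power of the written rule. The 0.880 behind the 12% reproduces only with OR futility; under the written AND the figure is about 0.95, so the comparison becomes 4% against about 5%. The Synopsis itself contains neither a 96% figure nor an NLR 0.15 scenario.

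**Conclusion.** The point holds as a misstatement of power, not as a calculation error or a shortfall in sample size. At NLR 0.20, sensitivity 0.90, specificity 0.50 and 20% prevalence, the stated 80% is about 5 points too low (OR futility) or 11.5 points too low (AND as written). At the same NLR and FNR, power is 0.52 (OR) or 0.63 (AND) at sensitivity 0.85, and 0.54 on either reading at sensitivity 0.95. The general claim of more than 80% power for FNR under 5% should not stand. At NLR 0.15 and sensitivity 0.90, Table 10's 0.96 is 8 points above Table 12, but only about 1 point above the power of the written rule.

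It is tempting to conclude that the Synopsis should now say about 85%, with a ceiling near 0.88 at sensitivity 0.90. That is premature: both figures depend on OR futility, which Section 9.5.1 does not state. The re-simulated values assume a binomial number of cases, looks at exactly 250 and 400, and sensitivity of at least 0.85 as the goal.

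**What to change.** 1. Reconcile the futility wording in Section 9.5.1 with Tables 12 and 13. If the written 'and' stands, rerun the simulation and replace both tables.
2. Then replace the 80% statements in the Synopsis and Section 9.2.1 with the simulated power of the full rule (both goals, both looks, adjusted score intervals, binding futility). Name the assumed NLR, sensitivity, specificity and prevalence.
3. Delete the sentence on FNR under 5%, or qualify it by sensitivity with a reference to Table 12.
4. Relabel Table 10 as NLR goal only, equation E, single look, sensitivity fixed at 0.90, and not the trial's power.

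The cost is wording, one table label and possibly a rerun of an existing simulation. No more participants are needed. The downside is that stated power becomes less favourable in some scenarios, notably at sensitivity 0.85 and 0.95.
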